1. PURPOSE

To determine the feasibility of establishing patient-derived organoids from pre-treatment rectal adenocarcinoma biopsies.

Primary Objective(s):

1. To determine the feasibility of establishing patient-derived organoids from pre-treatment rectal adenocarcinoma biopsies. The primary endpoint is the percent of biopsies that form spherical organoids.

Exploratory Objectives:

1. To describe the radiation response of patient-derived organoids and compare it to the patient's clinical response to neoadjuvant radiation.
2. To describe the radiation response of orthotopic organoid transplants in mice and compare it to the patient's clinical response to neoadjuvant radiation.
3. To describe the histopathologic and molecular characteristics of patient-derived organoids.

Hypotheses

1. 70% of patient-derived organoid attempts will be successful. This protocol will be hypothesis-generating. Data obtained from this protocol will guide future studies on the utility of patient-derived organoids for assessing radiation response in rectal cancer.

2. BACKGROUND AND SIGNIFICANCE

The standard of care for stage II-III rectal cancer is neoadjuvant chemoradiation or short-course radiation followed by total mesorectal excision.¹ Response to neoadjuvant radiation varies across patients, with some having minimal response to 10-30% having a pathologic complete response. Pathologic complete response is associated with improved clinical outcomes including resectability, sphincter preservation, local control, and overall survival.²⁻⁴ Predicting response to neoadjuvant radiation may inform prognosis and guide more individualized therapy.

Pretreatment markers including gene expression profiles and radiomic features have been investigated but are not used clinically due to limitations such as cost and generalizability.⁵⁻⁷ Preclinical models such as patient-derived tumor cell lines and xenografts have also been used to evaluate individual response to radiation.^{8,9} Limitations of patient-derived cell lines include loss of genetic heterogeneity due to inefficient generation and selective pressure as well as loss of tumor morphology in 2D growth conditions. Patient-derived xenografts retain genetic and phenotypic features, but also have limitations including high resource consumption.

Tumor organoids have emerged as another relevant preclinical model.¹⁰ Organoids grow in a 3D matrix, recapitulate tumor genetic and morphologic features, and have relatively efficient generation and expansion from patient tissue.¹⁰ The Hubrecht Institute generated patient-derived organoids from untreated colorectal cancer in 20 patients with an 80-90% success rate and

demonstrated similar morphology and somatic mutations between primary tumor biopsies and tumor organoids by H&E staining and whole exome sequencing.¹¹

More recently, several studies have explored the use of tumor organoids to predict response to chemotherapy and radiation, including three colorectal studies published in 2019. A study from the University of Wisconsin generated tumor organoids in multiple cancer types with a 76% success rate for colorectal cancer.¹² Seven primary tumors and corresponding organoids demonstrated similar morphology and mutations by next-generation sequencing, and colorectal cancer organoids had heterogeneous responses to 5-FU and radiation measured by organoid diameter and metabolic imaging. Additionally, as proof-of-principle, organoids from one patient with metastatic colorectal cancer were treated with 5-FU and oxaliplatin to predict whether the patient might respond to retreatment with FOLFOX.¹² Another study from Memorial Sloan Kettering generated rectal cancer organoids from 58 patients, both pre- and post-treatment, with a 77% success rate.¹³ Similar histopathology was demonstrated between primary tumors and corresponding organoids. To demonstrate preserved genetic heterogeneity in the organoids, the mutational landscape across 31 tumor organoids by targeted next-generation sequencing was shown to be similar to that of an independent rectal cancer cohort. Radiation of 19 rectal cancer organoids resulted in varying viability and dose-response curves. In six patients, organoid radiation response measured by the area under the dose-response curve appeared to correlate with patient radiation response measured by pre- and post-radiation tumor size on endoscopy. Four patient organoids were also engrafted into the mouse rectum to create a parallel preclinical model, and 5-FU and FOLFOX response of these transplanted organoids appeared to mirror clinical patient responses.¹³ Lastly, a study from Fudan University collected tumor samples from 112 patients with newly-diagnosed rectal cancer enrolled in a phase III trial (NCT02605265) evaluating the addition of irinotecan to neoadjuvant chemoradiation and generated organoids with a 86% success rate.¹⁴ In line with prior studies, similar histopathology was observed in primary tumors and organoids, and whole exome sequencing in 18 primary tumors and organoids demonstrated similar genomic alterations. For 80 patient-derived organoids, response to 5-FU, irinotecan, and radiation was measured by cell viability and organoid diameter and compared to patient clinical responses. Organoid response to at least one of the treatments generally correlated with patient's AJCC tumor regression grade. However, in 19 patients who had a good response to chemoradiation, the corresponding organoids were actually resistant to radiation, and the authors suggested that in the future, such patients might receive neoadjuvant chemotherapy alone.¹⁴

These studies using patient-derived rectal cancer organoids to model individual radiation responses are promising and merit further investigation. Our institution and the investigators on this protocol have experience in generating organoids from human colorectal tumor biopsies, endoscopy-guided transplantation of organoids in mice, and pelvic radiation in mice.¹⁵⁻¹⁸ Our institution also routinely evaluates and treats rectal cancer patients, from the initial work-up including proctoscopy to neoadjuvant radiation therapy for stage II-III patients to resection. Therefore, we believe that it would be feasible to generate patient-derived organoids from a rectal tumor biopsy obtained at proctoscopy. As proof-of-principle, we will also aim to measure the radiation response of these organoids *in vitro* and also of engrafted organoids in the mouse rectum *in vivo* and compare to patient clinical responses.

3. DESIGN AND PROCEDURE

For the primary objective, patient biopsies will be used to generate organoids as follows. One additional research biopsy will be obtained at the time of standard-of-care proctoscopy in clinic 3-2. The biopsy will be given a unique de-identified reference code. The de-identified biopsy will be placed in a sterile conical tube containing MACS Tissue Storage Solution (Miltenyi Biotec), then transported to [name] lab on wet ice by a research technician from [name] lab. [name] will generate spherical organoids from the research biopsy as previously described.¹⁹ Briefly, the biopsy will be manually minced with a razor blade or scalpel, transferred to a sterile conical tube containing enzymatic solution with Collagenase I (Roche), then spun in a MACSmix Tube Rotator (Miltenyi Biotec) in a 37°C incubator for 30-60 minutes. Then, the sample will be washed and centrifuged for 5 minutes, the supernatant will be discarded, and the tumor cell pellet will be resuspended in basal media and filtered through a 70 µm strainer. The cells will be counted, centrifuged again for 5 minutes, resuspended in a 1:1 Matrigel:PBS mixture (Corning), plated in a 24-well plate, and incubated at 37°C for 15-20 minutes, after which 1 mL media is added to each well. The cells will be assessed daily for organoid formation. Media will be changed every 3-4 days, and organoids will be passaged when the Matrigel reaches 80% confluence. Organoids will be passaged until the third passage, at which point the organoids will be transferred to [name].

For the exploratory objectives, the de-identified and passaged organoids will be given to [name] to assess the radiation response of organoids and organoid transplants. For organoid radiation response, plated organoids will receive a single fraction of radiation ranging from 0 – 15 Gy, then cell viability will be assessed by Resazurin assay to generate a radiation dose-response curve, and the AUC will be calculated. Designated members of the study team with access to the master log will be able to compare this organoid radiation response with the patient's clinical response to neoadjuvant radiation from the surgical pathology report.

For organoid transplantation, organoids will be gently dissociated and resuspended in 3D matrix with minimal medium and injected into the lamina propria of the mouse rectum as previously described.¹⁷ Transplanted tumors will be visible four to six weeks after injection.²⁰ Mice will then receive pelvic radiation of about 20-30 Gy in 4-5 fractions using a single arc, using previously described radiation methods.¹⁸ To measure radiation response, mice will be followed with periodic endoscopy and the percent change in tumor size index after radiation will be measured as previously described.²⁰ The tumor size index is the tumor area divided by the colorectal lumen area. Designated members of the study team with access to the master log will be able to compare the radiation response of organoid transplants with the patient's clinical response to neoadjuvant radiation from the surgical pathology report.

The last exploratory objective will be to describe the histopathology and molecular characteristics of patient-derived organoids. Histopathology may include hematoxylin and eosin staining as well as immunohistochemistry of markers such as CK20, CDX2, and β-catenin. Recent studies have demonstrated a diversity of morphologies in patient-derived organoids that appear to retain characteristics of the primary tumor.¹²⁻¹⁴ Molecular studies may include targeted next-generation sequencing and whole-exome sequencing. Recent studies have used high throughput sequencing to demonstrate that patient-derived organoids also preserve specific mutations compared to the primary tumor biopsy and also have similar total mutational loads and copy number variations.¹²⁻¹⁴ Any findings from organoid histopathology or molecular studies

will not be used for clinical intervention. Only designated members of the study team with access to the master log will be able to make any comparisons between organoid histopathology or molecular studies and patient histopathology or molecular studies.

This protocol involves collection of biopsy samples and analyses of data extracted from the electronic medical record. The variables, endpoint measures, and other data elements that will be extracted include:

- Duke MRN
- Date of birth
- Sex
- Race
- Pathologic diagnosis date
- Clinical TNM stage
- Pre- and post-neoadjuvant therapy proctoscopy findings
- Neoadjuvant radiation therapy dose, fractionation, and dates
- Neoadjuvant chemotherapy type, dose, and dates
- Surgery date
- Biopsy and surgical pathology findings including histology, microsatellite stability, genomic profiling (e.g. FoundationOne)

Eligible subjects are identified as described below in “Subject Recruitment and Compensation” section, and are selected for inclusion in subsequent analyses based on the criteria described below in the “Selection of Subjects” section.

Timeframe to complete subject identification: 24 months

Timeframe to complete data extraction and entry: 6 months

Timeframe to complete quality assurance check on extracted data: 1 month

Timeframe to complete data analyses: 3 months

Timeframe to complete manuscript and submission to journal: 12 months

Timeframe to disseminate conclusions via conference/meeting, if applicable: 6 months

Timeframe to protocol termination: 36 months

4. SELECTION OF SUBJECTS

The study population is patients with newly diagnosed, stage II/III rectal adenocarcinoma who are undergoing standard-of-care proctoscopy and planned neoadjuvant therapy (including neoadjuvant radiation) and total mesorectal excision. Patients who meet the criteria below will be approached for enrollment, and patients who consent or e-consent to this study will undergo an additional tumor biopsy at time of standard of care proctoscopy. If a patient is scheduled for a standard of care tumor evaluation in the endoscopy suite or the operating room and meets all eligibility criteria, the additional tumor biopsy may be obtained during the standard of care tumor evaluation. The target enrollment is 20 patients with stage II or stage III rectal cancer. We are requesting permission to consent up to 25 subjects to obtain an evaluable sample size of 20.

Inclusion

1. Age \geq 18 years old.
2. Able to provide informed consent; either paper or e-consent is permitted
3. Undergoing proctoscopy.

Exclusion

1. Patient not planned to receive neoadjuvant radiotherapy

5. SUBJECT RECRUITMENT AND COMPENSATION

Potential subjects with biopsy-proven stage II/III rectal adenocarcinoma (ICD-10 C20) or suspected stage II/III rectal adenocarcinoma with pending diagnostic biopsy be prospectively identified through MaestroCare.

Subjects will not be compensated for inclusion in this protocol.

6. CONSENT PROCESS

The informed consent form will be written in a manner that is understandable to the subject population. Prior to its use, the informed consent form and e-consent, if applicable will be approved by the IRB.

The Principal Investigator or authorized key personnel (other than [name]) will discuss with the potential subject the purpose of the research, methods, potential risks and benefits, subject concerns, and other study-related matters. Initial introduction of and any further discussions regarding the study will take place in an exam room in the Duke Cancer Center (for paper consent) or by telephone (for e-consent).

[name] MD PhD founded a start-up company called Xilis. Duke holds the IP license for microfluidic technology owned by Xilis that may be applied in analyses of the research samples collected on study. This potential COI will be disclosed to all future subjects in the revised ICF submitted via amendment to the IRB on March 21 2022.

Signing of the paper consent will occur in a private room in the Duke Cancer Center. All meetings and discussions regarding study participation will take place in a private room or by telephone. Potential subjects will have the opportunity to contact the Principal investigator or authorized key personnel with questions and have all questions answered before signing the informed consent.

For e-consent, the Research Nurse Study Coordinator will discuss the study with the subject and review the study consent by telephone. Subjects will provide an email address which will be used to generate and deliver the REDCap study consent form. Subjects are given the nurse coordinator's phone number to call with any additional questions or concerns. If the patient elects to participate, he/she will complete the consent via a secure REDCap link and select "Yes, I have read the consent form and I wish to participate in the study." Subjects who do not want to participate will select "Yes, I have read the consent form and I DO NOT wish to participate in

the study.” Patients may also review the e-consent and opt to sign a paper consent at their clinic visit.

Subjects will be given as much time as possible to make an informed decision about participation in the study. However, because consent will likely occur on the same day as the proctoscopy procedure, the amount of time available for consent review may be limited. Prospective subjects will be clearly informed of the voluntary nature of the study and freely allowed to decline participation.

The original informed consent form will be stored with the subject’s study records, and a copy of the informed consent form will be provided to the subject. The Principal Investigator or authorized key personnel will be responsible for asking the subject whether the subject wishes to notify his/her primary care physician about participation in the study. If the subject agrees to such notification, the Principal Investigator will inform the subject’s primary care physician about the subject’s participation in the clinical study.

7. STUDY INTERVENTIONS

This study will involve collection of additional tumor biopsy at time of standard-of-care proctoscopy for generation of patient-derived organoids, which are described in Design and Procedure section. No other clinical intervention will be performed.

8. RISK/BENEFIT ASSESSMENT

There is a certain amount of risk to collection of an additional biopsy, which is generally about 3-5 mm in size, for research purposes. Biopsy risk will be minimized by collecting the research biopsy at the same time as the standard-of-care proctoscopy procedure. The research biopsy will be collected at the treating physician’s discretion and only a single research biopsy sample will be obtained. There are also risks that privacy and confidentiality may be compromised. However, every reasonable effort will be made to limit breaches of privacy and confidentiality, as described in the “Privacy, data storage, and confidentiality” section below.

Subjects will not benefit directly from this protocol. However, data and conclusions derived from this protocol are expected to improve the current understanding of rectal adenocarcinoma and possibly influence future cancer patient care or cancer protocol designs.

9. COSTS TO SUBJECTS

This protocol does not involve any cost to subjects.

10. DATA ANALYSIS AND STATISTICAL CONSIDERATIONS

This is a specimen and clinical data collection protocol.

For the primary objective, all enrolled patients are evaluable, and we estimate the evaluable sample size will be 20 patient biopsies. For the exploratory objectives, evaluable patients are

those with successful patient-derived organoids, which we estimate will be about 14 of 20 initial biopsies.

Only descriptive statistical analyses will be performed. The primary objective will be reported as the percent of patient biopsies that form spherical organoids, and the 90% one-sided lower confidence limit will be reported. For instance, if we generate spherical organoids from 14 of 20 (70%) biopsies, the 90% one-sided lower confidence limit will be 56%. Laboratory procedures will follow group standard operating procedures (SOPs). Given the anticipated success rate of generating organoids of about 70%, if we are not successful at generating organoids from 3 of the first 5 patients, we will place the research protocol on hold, and all laboratory SOPs will be reviewed and modified.

The exploratory objectives will be described qualitatively given the anticipated small sample size.¹³ For the organoid radiation dose-response experiments, we will compare the dose-response AUC in patients who did or did not achieve a pCR. For the organoid transplantation experiments, we will compare the percent change in tumor size index in patients who did or did not achieve a pCR.

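### Is the 56% lower limit for 14 of 20 successes too favourable, because the exact binomial limit is 53%?

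*Combined protocol and SAP*

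**What the plan says.** Section 1 (Purpose) defines a single binomial proportion: "The primary endpoint is the percent of biopsies that form spherical organoids". Section 10 (Data Analysis and Statistical Considerations) plans for 20 evaluable biopsies ("we estimate the evaluable sample size will be 20 patient biopsies") and states that "the 90% one-sided lower confidence limit will be reported". It then gives one worked example: "if we generate spherical organoids from 14 of 20 (70%) biopsies, the 90% one-sided lower confidence limit will be 56" per cent.

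The same section sets the status of the analysis: "Only descriptive statistical analyses will be performed". Neither section attaches a null rate, a success threshold or a go/no-go rule to the limit. The one operational rule in Section 10, a hold after poor results in the first five patients, depends on a count and not on the confidence limit. No section names the interval method.

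**The concern.** With 20 observations, many statisticians would reach first for the exact binomial limit. For 14 of 20 that gives 53.3%, not 56%. Set against it, the printed figure looks wrong, and wrong in the optimistic direction. The suspicion grows when the binomial tail is computed: if the true rate were 56%, 14 or more successes would occur with probability 0.150, not 0.10, so the figure seems to carry 85% confidence under a 90% label.

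If that were right, it would matter. The limit is the only statement of uncertainty planned for the primary endpoint and the only precision figure that appears beside the sample size of 20. A reader might take it as the success rate that a later study can rely on.

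**Working it through.** **Inputs.** n = 20, x = 14, observed rate 0.70, one-sided 90% confidence, stated limit 56% (all Section 10). The normal quantile is z = 1.2816, so z² = 1.6424.

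**Step 1: reproduce the plan's figure.** The Wilson score lower limit is

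L = [p + z²/(2n) − z·√(p(1−p)/n + z²/(4n²))] / (1 + z²/n).

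- z²/(2n) = 1.6424/40 = 0.0411
- p(1−p)/n = 0.21/20 = 0.0105, and z²/(4n²) = 1.6424/1600 = 0.0010; the square root of their sum is 0.1074
- 1.2816 × 0.1074 = 0.1376
- L = (0.7000 + 0.0411 − 0.1376)/1.0821 = 0.558

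This rounds to 56%, so the plan's figure is reproduced.

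**Step 2: compare methods for 14 of 20, one-sided 90%.**

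| Method | Lower limit |
|---|---|
| Wald, 0.70 − 1.2816·√0.0105 | 56.9% |
| Jeffreys, 10% quantile of Beta(14.5, 6.5) | 55.9% |
| Wilson score | 55.8% |
| Agresti-Coull | 55.7% |
| Mid-P | 55.5% |
| Clopper-Pearson, 10% quantile of Beta(14, 7) | 53.3% |

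Three standard methods (Jeffreys, Wilson, Agresti-Coull) round to 56%. Plain Wald rounds to 57%, so the crude large-sample formula is not the evident source. The unrounded gap between Wilson and exact is 55.8 − 53.3 = 2.5 points.

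**Step 3: what the 85% is.** P(X ≥ 14 | n = 20, p = 0.56) = 0.150, and 1 − 0.150 = 0.850. The Clopper-Pearson limit is by definition the rate at which this tail equals 0.10. Any less conservative limit must give a larger tail, so failing this check shows only that the limit is not Clopper-Pearson.

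**Step 4: what the procedure delivers.** Coverage at a true rate p is the probability of a count whose limit does not exceed p.

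- At p = 0.56: the Wilson limit is 55.8% for 14 successes (covers) and 61.0% for 15 (misses). Coverage = 1 − P(X ≥ 15) = 1 − 0.066 = 93.4%. The exact limit has the same coverage here.
- At p = 0.70: the Wilson limit is 66.5% for 16 successes (covers) and 72.2% for 17 (misses). Coverage = 1 − P(X ≥ 17) = 1 − 0.107 = 89.3%. The exact limit for 17 is 69.6%, so it misses only from 18 upwards, and its coverage is 96.5%.

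Over a grid of 401 true rates from 50% to 90%, with n = 20:

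| | Average coverage | Lowest | At 70% |
|---|---|---|---|
| Wilson | 90.4% | 83.6% (near a true rate of 85%) | 89.3% |
| Clopper-Pearson | 94.0% | 90.0% | 96.5% |

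At the anticipated rate Wilson is 90 − 89.3 = 0.7 points below nominal and the exact limit is 96.5 − 90 = 6.5 points above it.

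**The case for a change.** The strongest case for a change has three parts.

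First, the method is unnamed, and the example does not identify it uniquely because Wilson, Jeffreys and Agresti-Coull all fit. This stands as an observation. But these three differ by only 0.2 points at 14 of 20 (55.7% to 55.9%), and the example rules out both the exact limit and plain Wald to the nearest per cent. The room left for a choice after the data are seen is small.

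Second, approximate limits do fall short in places. Coverage is lowest just below each attainable limit: at a true rate of 55.5%, Wilson covers 86.0%. It is under 90% over about 42% of the range from 50% to 90%. That is correct, and anyone who requires at least 90% at every true rate should use the exact limit. The plan sets no such requirement. Accepting average coverage near nominal instead of a guaranteed minimum is a recognised position, and the exact limit pays for its guarantee by over-covering.

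Third, the choice could shift how some results read. For 13 of 20, Wilson gives 50.7% and exact 48.2%; for 17 of 20, 72.2% and 69.6%. These pairs straddle 50% and the hypothesised 70%. But the plan does not compare the limit with either value, so no stated conclusion changes.

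**Conclusion.** The concern does not hold. The 56% is a correct one-sided 90% lower limit for 14 of 20 under standard methods, and the 53% comes from a more conservative method that the plan does not claim to use. The difference is 2.5 points before rounding. The 85% is a tail probability evaluated at one value. It does not describe the procedure, which covers 89.3% at the anticipated success rate and averages 90.4% over true rates of 50% to 90%. Preferring the exact limit is a matter on which competent statisticians differ.

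This conclusion assumes that the figure came from a Wilson-type limit. The documents do not say so; it is inferred from the match. If the source was Jeffreys, the printed 56% is equally correct, and coverage at 56% and at 70% is unchanged, because the Jeffreys limits for 14, 15, 16 and 17 successes (55.9%, 61.2%, 66.7%, 72.5%) fall on the same sides of those rates. The conclusion also rests on the limit remaining descriptive, as Section 10 states. The unnamed method is a minor missing detail that affects no enrolment, analysis or decision in the plan.

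### If the first-five hold leads to modified laboratory SOPs, must Section 10 plan a success rate for each SOP version?

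*Combined protocol and SAP*

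**What the plan says.** Section 1 (Purpose) gives the hypothesis that "70% of patient-derived organoid attempts will be successful" and describes the work as hypothesis-generating: "Data obtained from this protocol will guide future studies".

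Section 10 (Data Analysis and Statistical Considerations) defines the analysis set: "For the primary objective, all enrolled patients are evaluable, and we estimate the evaluable sample size will be 20 patient biopsies". The summary is a single figure: "The primary objective will be reported as the percent of patient biopsies that form spherical organoids". It carries a 90% one-sided lower confidence limit, illustrated as 56% for 14 of 20. Only descriptive analyses are planned.

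The same section contains the early check: "if we are not successful at generating organoids from 3 of the first 5 patients, we will place the research protocol on hold". In that event "all laboratory SOPs will be reviewed and modified". It does not say whether enrolment then resumes or how results would be laid out afterwards. SOP version is not among the data elements listed in Section 3 (Design and Procedure). Section 4 (Selection of Subjects) sets the numbers: "We are requesting permission to consent up to 25 subjects to obtain an evaluable sample size of 20".

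**The concern.** The plan provides for a change of procedure part-way through, then reports one proportion as if the procedure had been constant. After a hold, any later study would presumably use the modified SOPs. The all-enrolled percent would still include the biopsies whose failures prompted the change. If the modification worked, that percent would understate the success rate of the procedure carried forward.

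There is also a question of discretion. With 1 of 5 before the change and 12 of 15 after, the report could lead with 65% or with 80%, and the plan does not say in advance that both will be shown. As the data are meant to guide later work, it is reasonable to ask for a planned rate by SOP version.

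**Working it through.** **Inputs.** From Section 10: anticipated success rate 70%; hold after 3 failures in the first 5; 20 biopsies; 90% one-sided lower limit. From Section 4: at most 25 consents. Assumed here, because the documents do not give them: enrolment resumes; 5 biopsies use the old SOPs and 15 the modified ones; success is 40% before and 70% after.

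**The plan's own figure.** The one-sided Wilson limit with z = 1.2816 is [p + z²/2n − z√(p(1−p)/n + z²/4n²)] / (1 + z²/n). For 14/20 this is (0.7411 − 0.1376)/1.0821 = 55.8%, which matches the stated 56%. Section 10 names no method. Agresti-Coull (55.7%) and Jeffreys (55.9%) also round to 56%; Wald gives 56.9% and the exact limit 53.3%.

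**Chance of a hold.** Three or more failures in five is the same event as two or fewer successes, so P(hold) = P(X ≤ 2), with X binomial(5, p).
- p = 0.7: 0.0024 + 0.0284 + 0.1323 = 16.3%
- p = 0.6: 31.7%
- p = 0.5: 50.0%

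**All-enrolled percent given a hold.** The mean is (E[X | X ≤ 2] + 15 × 0.7)/20.
- 40% before, 70% after: E[X | X ≤ 2] = 0.9504/0.6826 = 1.392, so (1.392 + 10.5)/20 = 59.5%, a shortfall of 10.5 points from 70%.
- 70% throughout: E[X | X ≤ 2] = 0.2930/0.1631 = 1.796, so (1.796 + 10.5)/20 = 61.5%, a shortfall of 8.5 points.

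A shortfall of 8.5 points therefore arises when the procedures do not differ at all. Once a hold has occurred, lowering the earlier rate from 70% to 40% adds only 61.5 − 59.5 = 2.0 points. The split depends on the order taken: ignoring the hold, (5 × 0.4 + 15 × 0.7)/20 = 62.5%, so mixing gives 7.5 points and selection the other 3.0. Either way, the 10.5 points cannot be read as the cost of pooling two procedures.

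With 20 biopsies after the hold, the means are (1.392 + 14)/25 = 61.6% and (1.796 + 14)/25 = 63.2%, a difference of 1.6 points.

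**Using the later figure instead.** Given a hold, the later percent averages the true later rate. Suppose the modification has no effect, and the later percent is used after a hold and the all-enrolled percent otherwise. Over all trials the mean is P(hold) × p + {E[X; X ≥ 3] + P(no hold) × 15p}/20.
- p = 0.7: 0.1631 × 0.7 + (3.207 + 0.8369 × 10.5)/20 = 0.114 + 0.600 = 0.714
- p = 0.5: 0.5 × 0.5 + (1.719 + 0.5 × 7.5)/20 = 0.250 + 0.273 = 0.523

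With no effect of the modification, the all-enrolled percent averages exactly p.

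**Example and precision (Wilson).** With 1/5 then 12/15, all-enrolled is 13/20 = 65% (limit 51%) and the later group is 80% (limit 64%). At an observed 70%, the limit lies 14.2 points below the estimate with 20 biopsies and 16.5 points below with 15.

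**The case for a change.** The strongest case for a change is that the hold and the modification are the protocol's own contingency: it plans the laboratory response but not the reporting. Even at the anticipated 70%, a hold occurs about one time in six. Given a hold, the later percent has the right mean for the later procedure and the all-enrolled percent does not. Naming the split in advance would cost about two sentences and no patients, and would remove any choice between 65% and 80% in a case like the one above.

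Much of this stands. The documents plan no rate by SOP version, the arithmetic is right, and the before-and-after counts would be worth showing. What does not follow is that the plan is deficient without them. No test or decision rule rests on the final percent, and nothing prevents the breakdown. The hold rule is itself defined on the first five patients, which largely fixes where the cut would fall; biopsies still in culture at the hold would need a classification. The primary figure is fixed as the all-enrolled percent, so a later-group percent could not properly replace it.

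Nor should the later percent be prescribed as the planning figure. It is unbiased given a hold, but as a rule applied only after a hold it brings the upward bias shown above, and it rests on about 15 biopsies.

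**Conclusion.** No change follows. This is a gap in reporting detail that arises only after a hold (16% at a true 70% success rate, 32% at 60%, 50% at 50%), and only if enrolment then resumes, which the documents do not state. The all-enrolled percent answers the hypothesis in Section 1, is unbiased over all trials when the modification has no effect, and rightly remains the primary result. Following Section 10 as written gives a sound result.

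The 10.5-point shortfall depends on the assumed 5 + 15 split and the assumed 40% and 70% rates, and a shortfall of 8.5 points would occur with no difference between procedures. If a hold does occur, the team can log the SOP version per biopsy and show count, percent and lower limit before and after as a descriptive supplement. The first-five rate would then be low by selection, so the before-and-after difference could not be read as the effect of the SOP change.
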